## **Overview**

This protocol describes procedures for a study examining transcranial direct current stimulation (tDCS) combined with language treatment for individuals with aphasia following stroke.

---

## **PHASE 1: ELIGIBILITY TESTING**

### **Session Preparation**

- Prepare testing materials and record forms
- Start video/audio recording (label: Participant ID\_Eligibility Testing\_Date)
- Review test administration notes for any modifications

### **Participant Intake**

- Collect or administer Participant Intake Form via data collection system
- Collect Emergency Contact Information

### **Consent Procedures**

1. Review and obtain signed Informed Consent
2. Review and obtain signed HIPAA authorization
3. Provide participant with copies of signed forms
4. Collect payment information form

### **Screening Assessments**

#### **Frenchay Aphasia Screening Test**

- Administer all subtests per manual instructions
- Record: date, examiner, raw score, participant age

#### **Near Vision Screening**

- Ask participant to wear corrective lenses if needed
- Use Tumbling E chart
- Have participant identify direction of "E" on line 8 (or line 7 if needed)
- Pass criteria: Able to identify direction on line 8 or 7
- Record: whether participant wears glasses, pass/fail status

#### **Hearing Screening**

- Ask participant to wear hearing aids if needed

- Position participant facing away from audiometer
- Test frequencies: 1000, 2000, 4000, 500 Hz at 25dB and 35dB as needed
- Test order: Right ear (1000, 2000, 4000), Left ear (4000, 2000, 1000, 500), Right ear (500)
- Fail criteria: Cannot hear any tone at 35dB in either ear OR cannot hear any two tones at 25dB in same ear
- If participant fails, conduct informal speech discrimination screening
- Record: whether participant wears hearing aids, pass/fail for each ear

## **Language and Cognitive Assessments**

### **WAB-R (Western Aphasia Battery-Revised)**

Administer subtests:

- Conversational Questions
- Picture Description
- Auditory Verbal Comprehension (Yes/No Questions, Auditory Word Recognition, Sequential Commands)
- Repetition
- Object Naming
- Word Fluency
- Sentence Completion
- Responsive Speech

Record: date, examiner, subscale scores, aphasia quotient, aphasia type

### **CLQT+ (Cognitive Linguistic Quick Test Plus)**

Administer subtests:

- Personal Facts
- Symbol Cancellation
- Confrontation Naming
- Story Retelling
- Symbol Trails
- Generative Naming
- Design Memory
- Mazes
- Design Generation
- Auditory Comprehension
- Clock Drawing

Record: date, examiner, severity ratings for non-linguistic cognition, linguistic/aphasia indices, clock drawing

## **tDCS Head Measurement**

- Measure head circumference (1 inch above eyebrows and ears, on occipital bump)
- Take measurement twice for reliability
- Determine head strap size: Small (52-55 cm), Medium (55-58 cm), Large (58-62 cm)

---

## **PHASE 2: PRE/POST-TESTING**

### **Session Setup**

- Start recording (label: Participant ID\_Pre/Post Testing\_Date)
- Prepare testing materials

### **Assessments**

#### **Sentence Comprehension Task**

- Create copy of stimulus spreadsheet for this session
- Read each sentence aloud to participant
- Ask associated comprehension question
- Allow one repetition per sentence if requested
- Score: correct (1) or incorrect (0)
- Record repetition requests
- Calculate percent correct for each sentence type and overall
- Sentence types tested: anaphora, nominal grounding, clausal grounding, windowing, topicalization

#### **Revised Token Test**

- Administer Subtests 1-5 only (not pretest)
- Set up tokens according to specified arrangements for each subtest
- Before Subtest 3, provide explicit instruction and practice items with feedback
- Practice items: "Touch the blue circle and the red square," "Touch the black circle and the green circle," "Touch the red square and the blue circle"
- Record scores for each subtest and overall score

#### **Scenario Test**

- Administer using laminated stimulus cards
- Record: scores (0-3 scale), total score, percentile, communication modalities used, flexibility, partner assistance needs

## **Continuous Performance Task (CPT)**

- Administer on computer using experimental software
- Calculate: raw accuracy, average accuracy, average reaction time for non-target responses
- Export and save results data

## **Attention Network Test (ANT)**

- Set up response box with correct configuration
- Run practice trials until participant demonstrates understanding
- Administer full test
- Record: alerting effect RT, orienting effect RT, conflict effect RT
- Export and save raw and summary data

---

## **PHASE 3: tDCS ADMINISTRATION**

### **Device Setup**

1. Select appropriate tDCS device (pre-coded for participant)
2. Insert fully charged batteries (3 required)
3. Select correct head strap size based on eligibility measurements
4. Prepare two saline sponges

### **Application Procedure**

1. Seat participant comfortably
2. Clean scalp at electrode sites with alcohol wipes
3. Attach saline sponges to head strap electrodes using snaps
4. Position head strap on participant:
  - o Black electrode (labeled "front") on forehead
  - o Red electrode (labeled "top") on top of head
5. Ensure sponges are flush against scalp
6. Connect head strap to device (red to red, black to black)

### **Device Operation**

1. Power on device
2. Navigate menu: Select "Stimulation"
3. Check contact quality (aim for "good")
4. Enter session code
5. Device will begin automatically

### **During Stimulation**

- Monitor device for connection quality alerts
- Session duration: 20 minutes
- Device will beep when complete
- If participant needs to stop: Press zero to abort and ramp down current
- **Never remove head strap until current fully ramped down**

### **Post-Session**

- Remove head strap after current ramps down
- Remove batteries and recharge
- Dispose of sponges
- Clean head strap with alcohol wipes

---

## **PHASE 4: BEHAVIORAL TREATMENT SESSIONS**

### **Session Preparation**

- Access training stimulus materials
- Determine appropriate stimulus group for each sentence type based on previous performance
- Organize laminated stimulus cards in correct order
- Start recording (label: Participant #\_Training Session #)

### **Pre-Treatment Assessment**

- Administer Visual Analog Fatigue scale

### **Treatment Overview**

Introduce task: "I am going to read you some sentences and ask you some questions about them. Some sentences are challenging, and you may not get them correct on your first try. If you answer incorrectly, I will give you a cue and read you the sentence again. If you still get it wrong after the cue, I will give you the answer and we will move on."

### **Treatment Structure**

#### **Session cycle order:**

1. Anaphora
2. Nominal Grounding
3. Clausal Grounding
4. Topicalization
5. Windowing

Repeat cycle if time remains after completing all five types.

## **General Procedure for All Sentence Types**

### **For each sentence:**

1. Keep stimulus card hidden initially
2. Read sentence at steady pace
3. Wait 3 seconds
4. Ask comprehension question
5. If participant requests repetition: Repeat sentence without showing card, mark repetition
6. If incorrect: Provide one of three auditory cues while showing printed sentence
7. Remove card before re-asking question
8. If still incorrect after cue: Provide answer and move on

### **Auditory Cue Options:**

- **Self-monitoring:** "The next time I read the sentence, watch me, and make sure you are paying attention to what I am saying."
- **Rehearsal:** "I am going to repeat the sentence again. After I say it, I want you to repeat it either out loud or in your head before I ask the question."
- **Listening and anticipating:** "Think of the question I just asked you while I read the sentence again."

### **Scoring:**

- 1 point: Correct after initial question OR correct after repetition (no cues)
- 0 points: Incorrect or required any cues

## **Sentence Type Specifications**

### **Anaphora (Groups 1-3)**

- Single question per sentence
- **Advancement criterion:** 16+ correct responses over two consecutive trials

### **Nominal Grounding (Groups 1-3)**

- Instruct: "Please respond with Yes or No"
- Single question per sentence
- **Advancement criterion:** 16+ correct responses over two consecutive trials

### **Clausal Grounding (Groups 1-2)**

- Instruct: "Please respond with Yes or No"

- Single question per sentence
- **Advancement criterion:** 12+ correct responses over two consecutive trials

### Topicalization (Group 1)

- Two questions per sentence (Question A, then Question B)
- Read sentence before each question
- Follow standard cueing procedure for each question
- Score each question separately

### Windowing (Groups 1-3)

- **Group 1:** Three questions per sentence
- **Group 2:** Two questions per sentence
- **Group 3:** One question per sentence
- Read sentence before each question
- Participant does not need exact wording to be correct; use clinical judgment
- **Advancement criteria:**
  - Group 1→2: 48+ correct over two consecutive trials
  - Group 2→3: 32+ correct over two consecutive trials
  - Group 3: 16+ correct over two consecutive trials

### Advancement Rules

- If participant meets advancement criteria mid-session AND  $\geq 30$  minutes remain: Advance to next group
- If  $< 30$  minutes remain: Continue with current groups

### Post-Treatment Assessment

- Administer Visual Analog Fatigue scale

### Session Closing

1. Ask safety questions
2. Schedule next session if needed
3. Save session data
4. Enter data into system including:
  - Number correct and administered per category
  - Additional supports provided
  - Plan for next session

---

### Data Management

## **Recording Requirements**

- All sessions must be video or audio recorded
- Label recordings with: Participant ID, Session Type, Date

## **Data Entry**

- Enter all assessment scores into data management system
- Upload relevant files (Excel sheets, results files)
- Mark forms as complete after data entry

## **Test Administration Notes**

### **Frenchay Aphasia Screening Test:**

- Use larger pictures in examiner's manual
- Comprehension item #4: Score correct if participant points to left from picture's perspective
- Comprehension item #3: Say "rectangle" instead of "oblong"

### **WAB-R:**

- Yes/No Questions item #13: Use "Is this the Aphasia Lab?" (or appropriate location)
- Auditory Word Recognition: Substitute "painting" for "window" (item #37), "table" for "desk/bed" (item #39)
- Object Naming: Accept "cup" or "mug" as correct (item #4)
- Word Fluency: 1-minute time limit, start timer after giving directions

**Note:** Animal generation task appears in Frenchay, WAB, and CLQT. May use same data across tests.

---

## **Safety Considerations**

### **tDCS Safety**

- Never remove electrodes while current is active
- Monitor participant throughout stimulation
- Follow abort procedure if participant experiences discomfort
- Document any adverse events

### **General Safety**

- Ensure participant comfort throughout all procedures

- Offer breaks between assessment batteries
- Monitor for signs of fatigue
- Maintain appropriate infection control procedures

## Statistical Analysis

An intent-to-treat analytical approach will be used to examine differences in grammar scores between the two RCT arms. General and generalized linear mixed effect models (McCulloch & Neuhaus, 2001) for continuous and the dichotomized grammar measures, respectively, will be used to describe the pattern of change in each RCT arm and examine whether the pattern of change differs between RCT arms (i.e., significance of the treatment x time interaction). To account for potential heterogeneity between patients, each patient will be modeled as a random effect nested within treatment group. Time will be modeled as both a continuous and categorical variable defined by specific time points (baseline, post-training, follow-up). We will examine both within-patient changes (fixed time effect – to describe pattern of changes within each RCT arm) and between patient changes (fixed effect: time x treatment arm interaction – to examine whether pattern of change differs between RCT arms). Final models will be adjusted for (1) multiple comparisons using appropriate correction methods to adjust for inflation in the type I error rate and (2) missing data (possibly due to loss of follow-up) under the assumption that data are missing-at-random using a full information maximum-likelihood based approach (Collins et al., 2001).

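### For the continuous grammar measures with categorical time, the treatment x time test is valid but leaves the baseline mean free in each arm, which usually costs some precision

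*Combined protocol and SAP*

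**What the plan says.** All analysis text is in the Statistical Analysis section of the combined protocol and SAP. The aim is comparative: "An intent-to-treat analytical approach will be used to examine differences in grammar scores between the two RCT arms". Baseline enters as a level of time: "Time will be modeled as both a continuous and categorical variable defined by specific time points (baseline, post-training, follow-up". Two fixed effects are described. One is a "fixed time effect – to describe pattern of changes within each RCT arm". The other carries the arm comparison: "between patient changes (fixed effect: time x treatment arm interaction – to examine whether pattern of change differs between RCT arms". On correlation within patients, the plan says only that "each patient will be modeled as a random effect nested within treatment group". Missing data are handled "under the assumption that data are missing-at-random using a full information maximum-likelihood based approach".

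The adjustments listed for the final models are for multiple comparisons and for missing data. No baseline covariate, equal-baseline constraint or arm main effect is named. The baseline score will be available anyway: under "PHASE 2: PRE/POST-TESTING" the Sentence Comprehension Task tells staff to "Calculate percent correct for each sentence type and overall".

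**The concern.** With categorical time and baseline free in each arm, the interaction asks whether mean change from baseline differs between arms. In a randomised trial the arms share one baseline mean in expectation. The planned test does not use that fact. It subtracts the whole observed baseline imbalance, as if each unit of baseline difference carried forward in full. When the true slope of the later score on baseline is below 1, this over-corrects and adds noise.

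What is at stake is precision in the plan's only stated between-arm test, with data already to be collected. The mean model is also not written out in full, so two analysts could fit different models from the same text.

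**Working it through.** **Inputs.** From the Statistical Analysis section: two randomised arms, three time points, a patient random effect, and the treatment x time test. Not in the documents, so assumed: 1:1 allocation, total N of 20 or 40, two-sided 5% level, complete data, equal correlation rho between visits, and SDs equal across visits unless stated. The plan gives no power figure to reproduce.

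**1. What the planned contrast estimates.** A random-intercept model with arm x categorical time, fitted to complete simulated data, gave interaction coefficients of 0.7862 and 0.5747. The between-arm differences in mean change were 0.7862 and 0.5747. The contrast is therefore a change-score comparison.

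**2. Bias.** With a true difference of 0.5, simulated means were 0.497-0.503 for the change contrast and 0.497-0.502 with an estimated slope (N = 20, 40, 60; rho 0.3-0.97). Both are unbiased.

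**3. Variance per visit.** Let k be the post/baseline SD ratio. The large-sample ratio, adjusted to change, is k²(1-rho²)/(1+k²-2·rho·k). A common baseline mean with unstructured covariance gives the same large-sample values for k = 1, 1.2 and 1.5. For rho 0.5/0.7/0.8/0.9:
- k=1, where the formula reduces to (1+rho)/2: 0.75/0.85/0.90/0.95
- k=0.8: 0.57/0.63/0.64/0.61
- k=1.2: 0.87/0.97/1.00/0.98
- k=1.5: 0.96/1.00/0.95/0.78

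Estimating the slope multiplies these by 1+1/(N-4), which is 37/36 at N=40 and 17/16 at N=20. At k=1 and N=20 the ratio passes 1 when rho exceeds (N-5)/(N-3) = 15/17 = 0.88.

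**4. Power per visit against the planned model.** With equal SDs and correlations, the planned mixed model pools residual variance over 2(N-2) df. The adjusted contrast has N-3 df. At N=40, 80% power on 76 df needs noncentrality 2.838. At rho 0.5 the adjusted value is 2.838/√(0.75×37/36) = 3.232, which on 37 df gives 88%. At N=20 the same steps give 2.879/√(0.75×17/16) = 3.225 on 17 df, or 86%.

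**5. Joint test of both post-baseline visits (2 df).** The large-sample variance ratio is (1+2rho)/3 if the effect is the same at both visits: 0.667/0.800/0.867/0.933. It is (2/3)(1+2rho)/(1+rho) if the effect is at post-training only: 0.889/0.941/0.963/0.982. Power was simulated with 40,000 runs (planned F on 2 and 2(N-2) df, baseline-adjusted F on 2 and N-3 df). Null rejection was 0.046-0.051 for both tests.

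Adjusted power (%) when the planned test has 80%:

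| Comparison | rho 0.5 | 0.7 | 0.8 | 0.9 |
|---|---|---|---|---|
| Per visit, N=40 | 88 | 84 | 82 | 80 |
| Per visit, N=20 | 86 | 82 | 79 | 77 |
| Joint, effect persists, N=40 | 92 | 86 | 83 | 80 |
| Joint, effect persists, N=20 | 90 | 83 | 80 | 77 |
| Joint, post-training only, N=40 | 83 | 80 | 79 | 79 |
| Joint, post-training only, N=20 | 80 | 78 | 76 | 76 |

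A fully unstructured covariance with an exact F on 2 and N-4 df gives slightly lower joint power than these rows, mostly at N=20.

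**6. Why a random intercept alone will not do once the baseline mean is shared.** When SDs differ across visits, the variance ratio against the planned contrast is 0.88/1.00/1.05/1.11 at k=1.2 and 1.01/1.13/1.18/1.22 at k=1.5. The model-based variance is then only 0.86-0.90 and 0.72-0.80 of the true variance. A nominal 5% test becomes 2[1-Φ(1.96√0.90)] to 2[1-Φ(1.96√0.86)], about 6-7%, and by the same formula about 8-10% at k=1.5.

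**The case against.** Arm x time with baseline as an outcome is a standard repeated-measures analysis, and the test is valid. Nothing in the documents places this trial in the region of gain: N, rho, SDs and allocation are all unstated. If the effect fades by follow-up, the joint test, which is the like-for-like comparison with the planned interaction, gains only at N=40 with rho 0.5. At N=20 it is level at rho 0.5 and loses from rho 0.7. All of this stands, and it limits the point to an optional improvement.

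Unequal allocation can also reverse the result. With 1:3 allocation and slopes of 1.0 in the smaller arm and 0.2 in the larger, a single common slope gave a variance ratio of 1.44 even at N=400.

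A second objection is that moving baseline out of the outcome vector would discard something the plan wants. That is right. It would remove the description of change from baseline within each arm, and it would drop patients with only a baseline score, whom the planned likelihood keeps. The remedy below therefore keeps baseline as an outcome.

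Because no arm main effect is named, a reader might infer that the plan already shares the baseline mean. The listed terms allow that (rank 5 instead of rank 6). However, patients are nested in arm and change is described within each arm, so the ordinary reading has baseline free by arm.

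**Conclusion.** The point holds as a matter of efficiency and specification, at the level of a cheap improvement the sponsor could make. A reader might infer that the planned test is biased, or that the plan ignores baseline. Neither is supported: baseline is in the model as an outcome, and the interaction is unbiased under randomisation. Nor can one say that adjustment always helps, since the gain shrinks as the slope nears 1 and can turn slightly negative in a small trial.

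Under the stated assumptions, per-visit power rises from 80% to about 84-88% at N=40 for rho 0.5-0.7. It is unchanged at N=40 with rho 0.9 and falls to about 77% at N=20 with rho 0.9. The joint test gains clearly only if the effect persists. The actual size for this trial cannot be computed. The dichotomized measures and the continuous-time model are outside the claim, and these figures do not carry over to them.

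**What to change.** For the continuous measures with categorical time, write out the mean model:
- Keep baseline, post-training and follow-up in the outcome vector, and constrain the baseline mean to be equal in the two arms.
- Use an unstructured within-patient covariance, not a random intercept alone, with small-sample degrees of freedom. Robust standard errors would protect the error rate but not recover the precision.
- Report the arm differences at post-training and at follow-up, and test them jointly on 2 df.
- Fix the choice before unblinded data are seen.

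This keeps the within-arm description of change. It also keeps in the likelihood patients who lack a baseline score or have only a baseline score.

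Entering baseline score x time as a covariate is an acceptable alternative. It needs a second model for within-arm change and drops patients with no baseline or no post-baseline score. In that model arm x time alone tests only whether the arm difference changes between the two later visits, so the joint test must combine arm and arm x time.

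The cost is SAP wording, with no new data. The downsides are more covariance parameters and a possible small loss of power in a very small trial or if the effect does not persist. If N is near 20 and a high rho is expected, keeping the planned interaction is reasonable, provided its terms are stated. Baseline must also be measured unaffected by allocation; the documents do not say whether pre-testing comes before allocation, and the SAP should.
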